9.3 Investigator and Responsibilities	
9.4 Informed Consent Process	30
10 REFERENCES	31

PROTOCOL SYNOPSIS

Title	Epicardial Injection of Allogeneic Human Pluripotent Stem Cell-derived Cardiomyocytes to Treat Severe Chronic Heart Failure
Sponsor	HELP Therapeutics Co., Ltd. Nanjing, China
Objective	To evaluate the safety and efficacy of intramyocardial injection of Allogenic Human Induced Pluripotent Stem Cellsderived Cardiomyocytes in patients with severe chronic ischemic heart failure with coronary artery bypass grafting indications.
Principal Investigator	[name]
Institution	Nanjing Drum Tower Hospital
Indication	Severe Chronic Ischemic Heart Failure
Study Phase	Exploratory
Study Design	single-center, open-label, randomized controlled trial
Study Population	Patients with severe chronic ischemic heart failure with definitive coronary artery bypass grafting (CABG) indications.
Sample Size	20
Treatment Groups	This exploratory trial will enroll 20 patients with severe chronic ischemic heart failure who meet the inclusion/exclusion criteria. After providing informed consent, subjects will be randomized into two groups:
	Control Group (n=10): Patients will undergo standardized coronary artery bypass grafting (CABG) alone.
	Cell Therapy Group (n=10): Patients will receive CABG followed by intramyocardial cell therapy (2×10^8 cells). Following the completion of graft anastomoses, human-derived regenerative cardiomyocytes will be administered via 10 targeted injections into the peri-infarct region.
Follow-Up Schedule	Patients will undergo three scheduled visits at postoperative intervals of 1, 6, and 12 months. During each visit, relevant clinical documentation and laboratory test results will be recorded. Following the completion of the study follow-up period, subjects will transition into post-study safety surveillance, which will continue until either mortality or loss to follow-up occurs.

Primary Endpoints	Safety:					
	1. Incidence of sustained ventricular tachycardia (1~6 Month Post-operation)					
	O Defined as the proportion of patients experiencing ventricular tachycardia lasting more than 30 seconds					
	2. Incidence of newly formed tumors (12 Month Post-operation)					
	O By comparing chest, abdominal and pelvic CT scan and PET-CT scan					
Secondary Endpoints	Safety:					
	 Incidence of perioperative serious adverse events (SAEs): Such as Mortality, Non-fatal myocardial infarction, Stroke, Cardiac perforation, Cardiac tamponade, etc. Allogeneic immune monitoring: PRA, DSA (2 week, 1, 3, 6 and 12 Month Post-operation) 					
	3. Perioperative cardiac monitoring: (1 Month Post-operation)					
	Efficacy:					
	Left ventricular function assessment:					
	2. Six-minute walk test: o Distance walked measured at 6 and 12 months postoperatively.					
	3. NYHA functional classification: • Assessed at 6, and 12 months postoperatively.					
	 4. Quality of life evaluation: Minnesota Living with Heart Failure Questionnaire (MLHFQ) administered at 6, and 12 months postoperatively. 					
	5. Major adverse cardiac events (MACE) incidence: o Mortality; Non-fatal myocardial infarction; Heart failure-related rehospitalization					
Statistical Methods and Data Analyses	The trial results will be analyzed primarily using descriptive statistics.					

	Continuous variables will be presented as mean ± standard deviation, along with median, minimum, and maximum values. 95% confidence intervals for means will be estimated using the t-distribution method. Between-group comparisons of means will be performed using Student's t-test. Categorical and ordinal data will be summarized as frequencies (percentages) and rates. 95% confidence intervals for rates will be calculated using the Miettinen method. Between-group comparisons of proportions will be conducted using Fisher's exact test. Longitudinal comparisons (e.g., PRA, DSA, 6-minute walk distance, NYHA functional class, MLHFQ scores) will be analyzed using repeated measures ANOVA to assess dynamic changes over time.
Duration	2 years

.

LIST OF ABBREVIATIONS

iPSC	Induced pluripotent stem cells
HF	Heart failure
CABG	Coronary artery bypass graft
ICD	Implantable cardioverter defibrillator
LVEF	Left ventricular ejection fraction
LVEDV	Left ventricular end-diastolic volume
LVESV	Left ventricular end-systolic volume
MRI	Magnetic resonance imaging
CT	Computed tomography
cTnI	Cardiac troponin I
cTnT	Cardiac troponin T
CKMB	Creatine phosphokinase-Mb
NT-proBNP	N-terminalpro-brain natriuretic peptide
PCT	Procalcitonin
TSH	Thyroid stimulating hormone
ECG	Electrocardiogram
NYHA	New York Heart Association
MACE	Major adverse cardiac events
MLHFQ	Minnesota Quality of Life Questionnaire for Heart Failure
6MWD	6min walking test distance
PCI	Percutaneous coronary intervention
HLA	Human leukocyte antigen
PRA	Population reactive antibody
DSA	Anti-donor specific antibodies
CEA	Carcinoembryonic antigen
CA125	Glycogen 125

AFP	Alpha-fetoprotein
ADR	Adverse reactions
AE	Adverse events
SAE	Serious adverse events
CRF	Case report form
DSMB	Data and Safety Monitoring Board
EC	Ethics Committee
GCP	Good Clinical Practice
CI	confidence interval
ICF	Informed Consent Form
HIV	Human immunodeficiency virus
HCV	Hepatitis C virus
HBV	Hepatitis B virus
TP	Treponema Pallidum

Protocol (version 6.1)

Version data: 2021.08.01

Confidential
Page 10 of 38

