6.3 Sample Size Determination

This is an exploratory study. The total sample size is 20, with 10 allocated to the cell therapy group and 10 to the control group

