6.5 Statistical Analyses

6.5.1 Primary endpoint analysis

The primary endpoints, including incidence of sustained ventricular tachycardia (1~6 Month Post-operation) and newly formed tumors (12 Month Post-operation) will be analyzed using descriptive statistics (number of observations, mean, median, standard deviation, minimum, and maximum) for continuous variables and using frequencies and percentages for categorical and ordinal variables. A final analysis will be conducted when all subjects have completed the study participation.

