6.5.2 Secondary endpoint analysis

Secondary endpoints were analyzed using descriptive statistics. The comparative assessment of treatment effects employed distinct analytical approaches based on variable characteristics. Continuous variables are presented with mean, standard deviation, median, maximum and minimum values, and range, compared using the t-test method. Categorical and ordinal data are reported as frequencies (percentages), compared using the Wilcoxon rank-sum test. A two-sided p-value of ≤ 0.05 was considered statistically significant for all analyses.

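### The synopsis and section 6.5.2 name different tests for binary proportions, and at 10 v 10 the choice can change the verdict; naming Boschloo's exact test would settle it and gain some sensitivity at little cost

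*Protocol*

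**What the plan says.** The protocol describes the comparison of proportions in three places.

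- **Synopsis, Statistical Methods and Data Analyses.** The general approach is "The trial results will be analyzed primarily using descriptive statistics". For proportions, "Between-group comparisons of proportions will be conducted using Fisher", with the exact test named in the words that follow. No significance level is given there. It adds that "95% confidence intervals for rates will be calculated using the Miettinen method", without saying whether this means each arm's rate or the difference.
- **Section 6.5.1.** The two primary safety endpoints, sustained ventricular tachycardia and new tumours, are summarised "using frequencies and percentages for categorical and ordinal variables". No between-group test is named.
- **Section 6.5.2.** For secondary endpoints, "Categorical and ordinal data are reported as frequencies (percentages), compared using the Wilcoxon rank-sum test", and "A two-sided p-value of ≤ 0.05 was considered statistically significant for all analyses".

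Section 6.3 fixes the size: "The total sample size is 20, with 10 allocated to the cell therapy group and 10 to the control group". It calls the study exploratory and gives no event rate, effect size or power.

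**The concern.** A binary secondary endpoint, such as the proportion with a perioperative serious adverse event or with MACE, falls under both sentences. The synopsis gives it Fisher's test and 6.5.2 gives it the rank-sum test. In a large trial the two would rarely part company. At 10 v 10 they can, because Fisher's conditional test is very discrete at this size and the asymptotic rank-sum test is less so.

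The main proportions in this trial are harms. A test that leaves most of its permitted error rate unused is slow to flag an excess of harm in the cell arm, and analysts following different sections could label the same table differently.

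**Working it through.** **Inputs.** 10 v 10 (section 6.3), Fisher (synopsis), rank-sum and two-sided p ≤ 0.05 (section 6.5.2). The protocol has no power or error-rate figure to reproduce. Event rates below are assumptions.

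**Step 1: the table 4/10 v 0/10.**
- Fisher, two-sided: 2 × C(10,4)/C(20,4) = 2 × 210/4845 = 0.087.
- Fisher at 5/10 v 0/10: 2 × 252/15504 = 0.033, so against zero events it needs at least five.
- Asymptotic rank-sum: pooled z = 2.236, times √(19/20) = 2.18, p = 0.029. With continuity correction, p = 0.034.
- Exact rank-sum on binary data is the same test as Fisher: 0.087.
- Boschloo (ordered by the two-sided Fisher p-value): 0.042, from step 2.

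**Step 2: maximum error rate.** With a common event rate p, the rejection probability is the sum over rejecting tables (a, b) of Bin(a; 10, p) × Bin(b; 10, p). For both exact tests the maximum over p is at p = 0.5, where each table has weight C(10,a) × C(10,b)/2²⁰.
- Fisher rejects in 34 of 121 tables: 13,400/1,048,576 = 1.28%. At lower common rates the figure is 0.11% (rate 10%) and 0.76% (rate 20%).
- Boschloo adds 4 v 0, 6 v 1, 7 v 2, 8 v 3, 9 v 4 and 10 v 6, plus their mirror images. Their weight is 2 × (210 + 2100 + 5400 + 5400 + 2100 + 210) = 30,840. The total is 44,240/1,048,576 = 4.22%, in 46 tables, with no Fisher rejection lost.
- The asymptotic rank-sum test, with or without continuity correction, rejects in exactly the same 46 tables, so it differs from Fisher in 46 − 34 = 12.

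**Step 3: power with complete 10 v 10 data.** The sum is the same, with different rates in the two arms.

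| Assumed rates | Fisher | Boschloo |
|---|---|---|
| 40% v 5% | 24% | 43% |
| 30% v 2% | 12% | 29% |
| 20% v 0% | 3% | 12% |

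The last row can be checked by hand: with no control events, Fisher needs five or more (P = 0.033) and Boschloo four or more (P = 0.121) from Bin(10, 0.2).

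**Step 4: one control patient missing (4/10 v 0/9).** Fisher gives 0.087 and Boschloo 0.065, both non-significant. Barnard's test gives 0.034. Boschloo by doubling the one-sided p-value gives 0.052. So the unconditional tests, which agree at exactly 10 v 10, no longer agree. If the missing patient is in the cell arm (4/9 v 0/10), Fisher is already significant at 0.033.

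**The case against.** Fisher's test is standard and valid, and attained size below nominal is a known property of it. A reader might infer that the protocol promises a 5% error rate and delivers 1.3%. It does not: 0.05 in section 6.5.2 is a p-value cut-off, an upper bound that Fisher respects, and no attained rate is stated anywhere.

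A reader might also infer that the low sensitivity applies whichever section governs. It does not. If 6.5.2 governs and the rank-sum test is run in its asymptotic form, the rejection region at 10 v 10 is already Boschloo's. Only the synopsis's Fisher, or an exact rank-sum test, has the low sensitivity.

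A third tempting inference is that a real harm signal would be dismissed. The documents do not support that. Section 6.5.1 names no test for the primary endpoints, section 6.5.3 reports numbers of events and of subjects, and no stopping rule or other decision is tied to a p-value. Four events against none would be visible as such.

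Nor can the interval be said to contradict the Fisher p-value, because the synopsis speaks of intervals for rates and does not say that the difference is meant.

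Finally, sample size is the main limit: at 20% v 0% even Boschloo has only 12% power. The choice of exact test can also be refined in a statistical analysis plan, which is not shown here.

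All of this stands and limits the consequence. It does not remove the conflict, because the protocol itself commits to two different tests for the same kind of data.

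**Conclusion.** A cheap improvement is available. The synopsis and section 6.5.2 disagree on the test for binary secondary endpoints. At 10 v 10 this changes the 5% verdict in 12 of 121 tables if the rank-sum test is asymptotic, and in none if it is exact; the protocol does not say which.

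Of the two tests named, Fisher is valid but has a maximum error rate of 1.3%. Boschloo's test stays within 5% (4.2%), rejects wherever Fisher does, and nearly doubles power at assumed rates of 40% v 5%.

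These figures rest on complete data in both arms, independent binomial outcomes and assumed event rates. The gain shrinks with unequal arms, and at 10 v 9 the 4 v 0 table stays non-significant. The practical consequence is small in an exploratory, mainly descriptive trial.

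**What to change.** Reconcile the synopsis and section 6.5.2 in one edit:

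- Name one test for every between-group comparison of a binary proportion: Boschloo's unconditional exact test, two-sided, ordered by the two-sided Fisher p-value, at 0.05.
- Keep the Wilcoxon rank-sum test for ordinal data only.
- Do not write Boschloo or Barnard as alternatives. After a single dropout they can give opposite verdicts, which would leave the analyst a choice that decides the result.

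The cost is a sentence in each place and a software option, with no extra patients or data. The downside is a less familiar test that flags differences somewhat more often than Fisher, still within the 5% ceiling.

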2.2.2 Secondary endpoints

Efficacy:

- 1. Cardiac MRI Assessment of Left Ventricular Function:
 - o Comparative analysis of baseline versus postoperative measurements at 6, and 12 months, including: Infarcted size; End-diastolic lateral wall thickness; Focal septal thickness; Ejection fraction; End-diastolic volume; End-systolic volume; Stroke volume; Cardiac output; Myocardial density; End-diastolic myocardial mass
- 2. Echocardiographic Evaluation of Left Ventricular Function:
 - o Comparative analysis of baseline versus postoperative measurements at 6, and 12 months, including: End-diastolic septal thickness; Left ventricular end-diastolic

diameter; Left ventricular end-systolic diameter; Left ventricular posterior wall thickness at end-diastole; Left atrial diameter; Left ventricular ejection fraction; Mitral inflow velocity profile (E/A ratio)

- 3. Myocardial Perfusion Imaging (PET/ECT):
 - o Comparative analysis of left ventricular perfusion at preoperative, 6-month, and 12-month postoperatively
- 4. Six-Minute Walk Test (baseline, 6 and 12 months)
- 5. NYHA Functional Classification (baseline, 6 and 12 months)
- 6. Minnesota Living with Heart Failure Questionnaire (MLHFQ) (baseline, 6 and 12 months)
- 7. Incidence of Major Adverse Cardiac Events (MACE) including: Mortality; Non-fatal myocardial infarction; Heart failure rehospitalization

Safety:

- 1. Incidence of Perioperative Serious Adverse Events (SAE) Incidence: Mortality; Nonfatal myocardial infarction; stroke; cardiac perforation; cardiac temponade, etc.
- 2. Alloimmune Response Monitoring (PRA, DSA): (baseline, 1, 6 and 12 months)
- 3. Perioperative Electrocardiographic Monitoring (Within 1 month postoperatively)
- 4. Laboratory Tests, including Complete blood count, Comprehensive metabolic panel; NT-proBNP;Troponin; Myocardial enzyme profile; Procalcitonin; Immunological panel (C3, C4, IgA, IgG, IgM); Coagulation profile, etc.

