3.2 Exclusion Criteria

- 1. PRA \geq 20% or DSA-positive.
- 2. Previous implantation of ICD, CRT or similar treatment.
- 3. Valvular heart disease or received heart valvular disease
- 4. Previous percutaneous transluminal coronary intervention (PCI)
- 5. Atrial fibrillation
- 6. History of sustained ventricular tachycardia or sudden cardiac death.
- 7. Baseline glomerular filtration rate <30ml/min/1.73m2.
- 8. Liver dysfunction, as evidenced by enzymes (AST and ALT) greater than three times the ULN.
- 9. Hematological abnormality: A hematocrit <25% as determined by HCT, white blood cell<2500/ul or platelet values <100000/ul without another explanation.
- 10. Known, serious radiographic contrast allergy, penicillin allergy, streptomycin allergy.

Protocol (version 6.1)

Version data: 2021.08.01

Confidential
Page 18 of 38

- 11. Coagulopathy (INR>1.3) not due to a reversible cause.
- 12. Contra-indication to performance of an MRI scan.
- 13. History of organ transplant.
- 14. Clinical history of malignancy within 5 years (patients with prior malignancy must be disease-free for 5 years).
- 15. Non-cardiac condition that limits lifespan <1 year.
- 16. Chronic therapy with immunosuppressant medication, such as glucocorticoids and TNF α antagonist.
- 17. Patients' allergy to or contra-indication to immunosuppressants.
- 18. Serum positivity for HIV, HBV, HCV, TP.
- 19. Currently enrolled in other investigational therapeutic or device study.
- 20. Female patient who is pregnant or breast-feeding.
- 21. Other conditions that researchers consider not suitable to participate in this study.

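### DSA is listed for repeated-measures ANOVA, although the protocol treats it only as positive or negative and admits only negatives; a count of newly positive subjects would serve better

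*Protocol*

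**What the plan says.** The statistical methods cell of the Protocol Synopsis gives examples of longitudinal comparisons. The list opens with PRA and continues "DSA, 6-minute walk distance, NYHA functional class, MLHFQ scores) will be analyzed using repeated measures ANOVA to assess dynamic changes over time".

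The same cell has a separate rule for categorical data: "Categorical and ordinal data will be summarized as frequencies (percentages) and rates", then "95% confidence intervals for rates will be calculated using the Miettinen method", then "Between-group comparisons of proportions will be conducted using" Fisher's exact test. That rule names no variables.

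Section 6.5.2 mentions no repeated-measures ANOVA. It says: "Categorical and ordinal data are reported as frequencies (percentages), compared using the Wilcoxon rank-sum test".

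Exclusion criterion 1 in section 3.2 gives PRA a numeric limit and DSA none; it ends "20% or DSA-positive". No titre, intensity or other DSA unit appears anywhere in the protocol.

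On timing, section 2.2.2 has "Alloimmune Response Monitoring (PRA, DSA): (baseline, 1, 6 and 12 months", and the DSA row of Table 3 agrees. The synopsis has "Allogeneic immune monitoring: PRA, DSA (2 week, 1, 3, 6 and 12 Month Post-operation", but Table 3 contains no month-3 visit.

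**The concern.** New donor-specific antibody is a direct read-out of a risk the protocol itself names. Section 8 puts immune-mediated rejection among the primary risks, and section 4.1.1 ends the oral immunosuppressants at postoperative day 28. The clinical question is how many patients became positive after receiving the cells.

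Repeated-measures ANOVA compares visit means and relies on roughly normal residuals with a stable covariance across visits. A yes/no measure that is zero for everyone at baseline does not meet this. The variance is exactly zero at the first visit, and zero throughout in any arm where nobody converts. The test named for DSA could then return nothing when the result is reassuring, or too small a p-value when a few patients convert and stay positive.

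**Working it through.** The protocol gives no figure for this analysis, so there is none to reproduce. The check asks how the named test behaves on yes/no data.

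**Inputs**
- 10 subjects per arm (section 6.3).
- Four visits: baseline and months 1, 6 and 12 (section 2.2.2, Table 3).
- All subjects negative at baseline (section 3.2, criterion 1).
- Two-sided 0.05 (section 6.5.2).
- Assumptions: DSA is scored 0/1 at follow-up; converters turn positive by month 1 and stay positive. Conversion rates are illustrative.

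**Group-by-time test.** Let *a* subjects convert in the cell arm and *b* in the control arm. A converter's scores are 0, 1, 1, 1, with within-subject sum of squares 3/4.
- Interaction SS = (3/4) × 5 × ((a−b)/10)², on 3 df.
- Error SS = (3/4) × [a(10−a) + b(10−b)]/10, on 18 × 3 = 54 df.
- F = 9(a−b)² / [a(10−a) + b(10−b)]. With b = 0 this is 9a/(10−a).

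**No converters.** With a = b = 0, F = 0/0. At a true rate *r* in both arms the chance of this is (1−r)^20: 67%, 36% and 12% for r = 2%, 5% and 10%. If only the cell arm can convert it is (1−r)^10: 82%, 60% and 35%.

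**A few persistent converters, none in controls.** The scores follow a single pattern over time, so the Greenhouse-Geisser epsilon is 1/3 and the corrected df are 1 and 18.

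| Converters | F | Uncorrected p (3, 54 df) | Corrected p (1, 18 df) | Fisher p |
|---|---|---|---|---|
| 1/10 vs 0/10 | 1.00 | 0.40 | 0.33 | 1.00 |
| 2/10 vs 0/10 | 2.25 | 0.093 | 0.15 | 0.47 |
| 3/10 vs 0/10 | 3.86 | 0.014 | 0.065 | 0.21 |
| 4/10 vs 0/10 | 6.00 | 0.001 | 0.025 | 0.087 |

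**False-positive rate.** This sums two independent Binomial(10, r) counts over every outcome with p ≤ 0.05, taking an undefined F as not significant.

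| True rate in both arms | Uncorrected | Corrected | Fisher |
|---|---|---|---|
| 5% | 1.4% | 0.1% | 0.0% |
| 10% | 5.0% | 0.9% | 0.1% |
| 20% | 9.1% | 3.0% | 0.8% |
| 30% | 10.0% | 3.7% | 1.2% |

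The uncorrected test reaches the nominal level at a rate of about 10% in both arms and clearly exceeds it at 20–30%. The corrected test stays below it throughout this range.

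**Transient converters.** Let *m* different cell-arm patients each be positive at one visit only, spread evenly over the three post-operative visits. The ANOVA's between-group effect is F = 9m/(10−m) on 1 and 18 df. For m = 6, F = 13.5 and p = 0.0017; for m = 9, F = 81 and p = 4 × 10⁻⁸. The interaction alone gives p = 0.59 and 0.40.

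**What a count would show.** Exact 95% intervals are 0–31% for 0/10, 2.5–56% for 2/10 and 6.7–65% for 3/10. The Miettinen-Nurminen difference for 3/10 versus 0/10 is 30% (−3% to 61%).

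**The case against.** The strongest reply is that the premise is unproven. A numeric assay result can be dichotomised for eligibility, and listing DSA beside PRA, walk distance and a questionnaire score fits a numeric follow-up measure. This stands, and it makes the point conditional.

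Second, sphericity correction is ordinary analysis-plan detail, and the protocol does not say that the test is uncorrected. The inflation also needs substantial conversion in both arms, while controls receive no cells. Both parts stand: inflated error is a possibility under stated conditions, not an expected outcome. A reader might reach for a still higher rate by counting all the synopsis time points, but Table 3 schedules DSA at four visits only.

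Third, a reader might infer that ANOVA would miss many transient converters, because the interaction p-value is large. The documents do not confine inference to the interaction, and the group effect of the same analysis detects them strongly. That reading is not supported.

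Fourth, the synopsis calls the analysis mainly descriptive, its longitudinal list is illustrative, and its categorical rule would cover a yes/no DSA without naming it. It is fair that no analysis is absent and that an undefined F with no converters misleads nobody. But DSA is one of the examples expressly given for ANOVA, and the categorical rule does not say which count applies: one visit, each visit or any visit.

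**Conclusion.** The point holds as a minor one, conditional on DSA being recorded as positive or negative after surgery. Then the named test fits the data poorly. It has no value when nobody converts, and without correction it gives p=0.014 for three persistent converters where Greenhouse-Geisser gives 0.065 and Fisher 0.21. Correction removes the excess false positives, but not the undefined result.

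The protocol does not establish that follow-up DSA is binary or that the ANOVA will be uncorrected. The conversion rates and persistence pattern used here are assumptions. DSA is a secondary safety measure in an exploratory trial of 20, and no stated decision depends on this test.

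**What to change.** Take DSA off the repeated-measures ANOVA list in the synopsis. Add one sentence: the number and percentage of subjects per arm newly DSA-positive at any post-operative visit will be reported with an exact or Miettinen 95% confidence interval and compared by Fisher's exact test, next to by-visit counts and a per-subject listing. State the same test for this count in section 6.5.2, which otherwise points to Wilcoxon. If DSA is recorded as a numeric level, keep ANOVA as a description of the trajectory and add the count.

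The cost is a small text change and no new data. There are two downsides. Fisher's test is weak with few events (4/10 versus 0/10 gives p=0.087), so the gain is a valid, visible estimate rather than power. An any-visit count also treats one transient positive like a persistent one; the by-visit counts and the listing preserve that difference.
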